Aim 1: To identify Veteran and surgeon factors associated with preference for endovascular or open repair. We will use validated survey instruments to determine repair type preference (endovascular or open) for Veterans and surgeons, and identify domains in our survey associated with each repair type.

Hypothesis (H1): We hypothesize Veterans who prioritize concerns about pain or disability will prefer endovascular repair, and Veterans who prioritize concerns about durability will prefer open repair.

Aim 2: To determine the effect of the decision aid on agreement between preference and repair type. AAA growth rate estimates suggest 85% of our cohort will undergo repair within our two – year study period. Among patients in the intervention and control groups who undergo repair, we will compare how commonly Veterans receive the repair type they indicated as their preference. We will study potential explanatory variables from our survey, such as AAA knowledge, between the intervention and control groups. Patient satisfaction and shared decision making will be assessed in both the intervention

and control groups.

Hypothesis (H2): Our intervention will be associated with better agreement between preference and treatment type for Veterans with AAA, as well as higher post-operative satisfaction and greater shared decision-making.

2. Study Team

[name], the Principal Investigator, is a VA vascular surgeon and Co-Director of the VA Outcomes Group in White River Junction. A current NIH K08 awardee in health services research, he is experienced in conducting multicenter, cluster-randomized clinical trials^{61, 62}. He is currently the Principal Investigator of a multicenter cluster-randomized trial of a smoking cessation quality improvement intervention funded by the Society for Vascular Surgery⁶². [name] has assembled a team (Table 1) with extensive expertise in survey research ([name]), shared decision-making ([name]), and analyzing outcomes in VA (Drs. [name] and [name]). Finally, [name] and his team members have worked together before in several projects^{63, 64}, many of which have studied physician practice⁶⁴⁻⁶⁶, so they are well prepared to collaborate effectively in this study. Their team, including 20 site PIs, have collaborated on several projects which have studied physician practice⁷¹⁻⁷³ and each has significant time dedicated towards the proposal.

Table 1: Key Personnel

Team Member	Role	Skill Set	Task Aims

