To identify patient characteristics (such as survey responses) associated with preference for endovascular or open repair we will use multivariable mixed effects logistic regression. The use of mixed effects is to account for clustering within individual VA centers using a random intercept, e.g. $\text{logit } \text{Pr}[Y_{ij}=1]=X_{ij}\beta+\mu_i$ where Y_{ij} is the binary preference variable in subject j from cluster i , X_{ij} is a vector of characteristics, μ_i is a random intercept from a zero mean distribution with standard deviation to be estimated (e.g. normal), and β is a vector of coefficient(s). We will explore the feasibility (e.g. convergence) and sensitivity of findings of patient characteristics of using either a random intercept for surgeon, or for center, or for surgeon nested within center. We will report both unadjusted and adjusted estimates, after identifying one or more models to adjust for using for instance stepwise regression or LASSO. Stata (e.g., xtmelogit) and/or R (library lme4 or nlme) software will be used. [name] has extensive experience in these strategies.

Missing Data: To accommodate missing data where justified (e.g. the variable with missing data is predictive and deserves to be adjusted for, and furthermore the data is believed to be missing at random) we shall use multiple imputation methods, such as implemented in the Stata *mi* routine.

Power Analysis: Comparing the effect of the decision aid on repair type preference. Because the decision aid will inform Veterans more fully about the long-term disadvantages of endovascular repair, we hypothesize that the decision aid will reduce the proportion of Veterans who prefer endovascular repair by 25%, based on similar decision aids studied in surgical settings in breast cancer and back pain¹⁶⁻¹⁸.

Table 3 Sample size and power calculations (assuming a 90% baseline rate of EVAR preference)

Number of clusters	Number of patients per cluster	Total Number of Patients	Proportion Choosing Endovascular Repair At	Decision Aid Effect Size (in relative decline in preference)	Proportion Choosing Endovasc Repair at	Power To detect significant difference	Power To detect significant difference	Power To detect significant difference
--------------------	--------------------------------	--------------------------	--	--	--	--	--	--

Intervention	Control	Intervention	Control	Intervention	Control	Control Sites for endovascular	Intervention Sites	(ICC 0.01)	(ICC 0.05)	(ICC 0.10)

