10	10	12	12	120	120	0.9	0.25	0.68	0.96	0.86
10	10	12	12	120	120	0.9	0.20	0.73	0.88	0.75
10	10	12	12	120	120	0.9	0.15	0.78	0.71	0.50

We adjusted our sample size calculations for our cluster-randomized trial to account for intra-cluster correlation, and allow for variable enrollment size within each cluster. As shown in Table 8, we anticipate that we will have 96% likelihood of detecting a 25% effect size, assuming an ICC of 0.01. Sensitivity analyses around our ICC assumption of 0.01 demonstrate that even if our ICC is ten times higher (ICC=0.10), our sample size would still yield an 81% likelihood of detecting a 25% effect size between intervention/control.

Aim 2: To determine the effect of the decision aid on agreement between preferences and repair type.

Aim 2 Dependent and Independent Variables: After identifying Veterans' preference for endovascular or open repair, we will determine the agreement between their preferences and the repair types they receive. The dependent variable will be the kappa statistic (κ), measuring agreement between the preferred repair type and the repair type the Veteran ultimately receives. Cohen's kappa will be compared between the intervention and control groups. Kappa will be calculated overall and by hospital (using a weighted sum of the kappas for each hospital in that arm). As a secondary outcome, Site Study Coordinators will administer two surveys to the Veteran. These two surveys will examine patient satisfaction (PDQ-18) and shared decision making (Decision Process Score, or DPS)^{87, 104}. Our group has used these or similar instruments in prior work^{104, 105}. A survey administration training guide for each Site Study Coordinator has been developed. The DPS will be administered at the end of the visit, and the PDQ-18 will be completed at 30-day follow-up visits which are already standard practice after AAA repair for both repair types. Completing the surveys in this context will not require any extra visits by Veterans, an important strength given the elderly population of patients involved in our proposal.

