Aim 2 Data Collection Strategy: potential problems and solutions: To inform the agreement between preference and repair type, we will compare the preference identified for each Veteran and the actual AAA repair type the Veteran receives at each site. We anticipate that 85% of Veterans will undergo repair within three months after the study visit in which they are enrolled. However, we estimate that 15% of patients will not undergo repair within 3 months of enrollment. Therefore, to ensure we capture the repair type for these patients, each Site Study Coordinator will audit CPRS every three months during the study period. At the end of the two years of audits, the site specific Site Study Coordinator will contact the enrolled patients via phone to ensure repair has not been performed outside of VA. Patients who do not undergo repair or who die prior to repair will be excluded. Sample size calculations incorporate a dropout rate of 10% for this effect. Re-survey will occur for a delay in repair greater than 3 months, if the pre-survey shows a change in Veteran repair preference from the original enrollment survey.

Aim 2 Data analytic strategy: After we have measured the necessary elements for agreement (preferences for repair type and the actual repair type), we will then calculate Cohen's kappa. We will stratify these analyses for surgeon agreement with the actual repair type (surgeon-preferred repair type matches the actual repair type, surgeon-preferred repair type does not match the actual repair type, and surgeon has no preference in repair type). Of note, Question #8 in the Decision Process Score allows us to measure incidents where discussion with the surgeon changed the Veteran's preference after the survey. We will perform sensitivity analyses including and excluding Veterans who changed preferences. To account for possible agreement of preference and choice with age, gender and race, we will estimate the association of choice with preference in a multivariable binary regression model that includes age, gender and race, and report the odds ratio (via logistic link) and rate ratio (via Poisson link). The fitted value from the logistic regression model will be used to calculate the four proportions used in the calculation of Kappa agreement using the method of average predictions (fitted values). Bootstrapping methods, as described by Efron and Tibshirani¹⁰⁶, will be performed if individual hospital samples are small.

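### Aim 2 compares kappa between arms, but kappa can move with the preference shift the decision aid is meant to cause, and the stated 80% power holds only for a one-sample test

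*Combined protocol and SAP*

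**What the plan says.** The Specific Aims put Aim 2 as a question of frequency: "we will compare how commonly Veterans receive the repair type they indicated as their preference". Section 7 (Aim 2 Dependent and Independent Variables) turns this into Cohen's kappa and states that "kappa will be compared between the intervention and control groups". It adds: "Kappa will be calculated overall and by hospital (using a weighted sum of the kappas for each hospital in that arm"; the weights are not given. Section 7 specifies no between-arm test of the proportion who receive their preferred repair.

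Under Aim 2 Data analytic strategy, the investigators will also "estimate the association of choice with preference in a multivariable binary regression model that includes age, gender and race". No arm term is named, although the Aim 1 comparison of preferences does name a group effect and a centre intercept. Then, "The fitted value from the logistic regression model will be used to calculate the four proportions used in the calculation of Kappa agreement". Bootstrapping "will be performed if individual hospital samples are small".

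The Aim 1 power section says "we hypothesize that the decision aid will reduce the proportion of Veterans who prefer endovascular repair by 25" per cent, from a 90% baseline; Table 3 prints 0.68 for the intervention sites. The Aim 2 power section takes kappa 0.70 and 0.88, a two-tailed test and a 50% positive rate, and reports 80% power at 101 per arm.

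**The concern.** Kappa corrects observed agreement for the agreement expected from the two margins. One of those margins is the preference split, which the aid is expected to change. If surgeons honour preferences exactly as before, kappa may still differ between arms, and the difference could be reported as better alignment. How far it moves depends on how often each preference is honoured (the chance that a Veteran receives the repair he or she prefers), and the documents do not state this.

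The power statement has its own difficulty. It describes a test against a fixed value, while the plan compares two estimated kappas, and its 50% split is not the one expected in either arm.

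**Working it through.** **Inputs.** Preference for endovascular repair (EVAR) is 0.90 in control and 0.90 × 0.75 = 0.675 with the aid (Aim 1 power section). There are 120 Veterans per arm, 12 per hospital. The Aim 2 power section names 10% dropout and 15% unrepaired: 120 × 0.90 × 0.85 = 92, or 120 × 0.85 = 102 if only the unrepaired are lost. The Aim 2 Data Collection Strategy says "Sample size calculations incorporate a dropout rate of 10% for this effect", which would leave 108; 92–102 is used here. Two-sided alpha of 0.05 is assumed, since none is stated. Honouring rates are assumed throughout.

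**1. The plan's 101.** With common margins, n × Var(κ) = V(κ,p) = (1−κ)[(1−κ)(1−2κ) + κ(2−κ)/(2p(1−p))]. At p = 0.5, V(0.70) = 0.510 and V(0.88) = 0.2256. As a one-sample test against 0.70, n = [1.96√0.510 + 0.842√0.2256]² / 0.18² = 99.9, close to the stated 101. At n = 101 the power is 80.6%.

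**2. The same contrast with two arms.** Power = Φ(0.18/√((V₀+V₁)/n) − 1.96).
- 50% split: V₀+V₁ = 0.7356, giving 52% at n = 92 and 56% at n = 102. About 178 per arm would be needed for 80%.
- 0.90 against 0.675: V₀+V₁ = 1.481 + 0.259 = 1.739, giving 26% and 28%. About 421 per arm would be needed.

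None of these figures allows for clustering.

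**3. Kappa with honouring unchanged.** κ = (po−pe)/(1−pe). At 90% honouring of both preferences:
- Control: EVAR received = 0.9×0.9 + 0.1×0.1 = 0.82; pe = 0.9×0.82 + 0.1×0.18 = 0.756; κ = 0.144/0.244 = 0.59.
- Intervention: EVAR received = 0.64; pe = 0.549; κ = 0.351/0.451 = 0.78.

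The table repeats this for other honouring rates. Its last column is the simulated share of trials in which a two-sample kappa test (|z| > 1.96, no clustering) favours the aid; with no preference shift it is about 3%.

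| Honoured, EVAR / open | κ at 0.90 | κ at 0.675 | Falsely favours aid |
|---|---|---|---|
| 85% / 85% | 0.46 | 0.67 | 34–37% |
| 90% / 90% | 0.59 | 0.78 | 28–31% |
| 94% / 94% | 0.73 | 0.87 | 17–20% |
| 94% / 80% | 0.64 | 0.75 | 11–12% |
| 92% / 25% | 0.17 | 0.20 | about 10% |
| 94% / 50% | 0.43 | 0.49 | about 7% |
| 97% / 73% | 0.70 | 0.74 | about 4% |
| 98% / 50% | 0.56 | 0.54 | about 3% |
| 99% / 50% | 0.60 | 0.56 | about 3% |

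With uniform honouring and Table 3's smaller declines, the figures are 15–31% (20% decline) and 12–24% (15% decline). With uniform honouring and a control preference of 80%, a 25% decline gives about 7–12%.

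**4. The regression, if pooled over arms without arm terms.** Veterans with the same preference and covariates get the same fitted probability in both arms. Suppose honouring rises from 85% to 95% with no preference shift. The true kappas are 0.46 and 0.76, but the pooled conditional rate is (85+95)/2 = 90% in both arms, so both fitted kappas are 0.59. Fitting by arm avoids this.

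**5. Hospital kappas.** Each hospital has 12 × 0.765 = 9.2 to 12 × 0.85 = 10.2 repaired Veterans. With 10, the chance that all prefer EVAR is 0.9¹⁰ = 35% in control and 0.675¹⁰ = 2% in intervention hospitals. Counting any constant margin, with honouring of 90–94% uniform or 97%/73%, kappa is 0/0 or forced to 0 in about 36–48% of control and 2–8% of intervention hospitals. Resampling cannot supply variation that the hospital lacks.

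**The case against.** Chance-corrected agreement is a defensible measure when one repair dominates, and the kappa contrast is between randomised arms. A comparison within preferred type conditions on something measured after the aid. This stands as a real limitation of the remedy. If Veterans moved to open repair by the aid were honoured 50% of the time and existing open-preferrers 80%, a test stratified by preferred type would show false harm in 11–12% of trials. With those rates reversed it would show false benefit in 12–14%.

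The 17–37% range is a corner case that needs both uniform honouring and a 90% control preference. That also stands. The Introduction's two preliminary interviews describe surgeons steering Veterans towards endovascular repair, which points, weakly, to unequal honouring and so to the lower figures. The 90% is nevertheless the plan's own assumption.

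The missing arm term may be only an omission. The regression is introduced to account for age, gender and race, and fitting it by arm is a natural reading. A reader might infer that the plan forces equal alignment on both arms; the text does not say so, and one sentence would settle it.

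The hospital problem depends on the unstated weights. With weights n(1−pe), 0/0 hospitals drop out and forced zeros carry about 13–17% of control weight. Mean control kappa is then 0.56 against a true 0.59 (90% uniform), or 0.67 against 0.70 (97%/73%). Weighting by n gives 0.50 and 0.60. Stated weights would reduce the distortion but not remove it.

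A reader might also infer that the whole planned effect is artefact, because 94.6% raw agreement in both arms takes kappa from 0.70 to 0.88 when only the split moves. With balanced margins, however, that implies honouring of open preferences rising from 1 − 0.027/0.10 = 73% to 1 − 0.027/0.325 = 92%, which is a real change.

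**Conclusion.** The concern holds in a limited form and should be fixed. Kappa can move with the preference shift, so a between-arm difference does not by itself show better alignment. The false-benefit rate ranges from close to nominal to more than one trial in three, depending on honouring rates that the documents do not give. They do not support saying that the comparison must be biased, or that it must favour the aid: in two of the unequal-honouring scenarios kappa falls slightly.

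The power finding does not depend on honouring rates. It rests on the plan's own kappas, a two-sided 5% level and common margins. The stated 80% belongs to a one-sample test, and the planned two-arm comparison has roughly half to a quarter power before clustering. The arm term and the hospital weights need only clarification.

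**What to change.** 1. Restate Aim 2 power as a two-arm comparison at the Aim 1 preference splits, after losses and with clustering.
2. Base inference on receipt of the preferred repair, compared by arm and stratified by or adjusted for preferred type. This can be a Mantel-Haenszel test, or logistic regression with arm, preferred type and a site random intercept. Report the proportion honoured by arm within each type. The pooled proportion alone is not enough: at unchanged 97%/73% honouring it falls from 94.6% to 89.2% when the split moves. A Mantel-Haenszel test that ignores clustering rejects in 8–10% of null trials at a honouring ICC of 0.05 and 12–14% at 0.10, so it needs an adjustment.
3. Name this common-effect test, not the arm-by-preference interaction. Without clustering its power is about 60–64% for honouring 85% to 95%, 45–50% for 90% to 97%, and 19–21% for open preferences only, 73% to 92%. The interaction has about 40–45%, 27–35% and 12–17%.
4. Keep overall kappa by arm as descriptive, shown with both margins. State that the regression is fitted by arm or includes arm terms.
5. Do not use the hospital-weighted kappa for inference. If it is reported, state the weights, such as n(1−pe).

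The cost is SAP wording and a new power statement, with no new data. The plan should also state the downsides. Preference is measured after the aid, so selection is possible. Only about 9–10 control Veterans would prefer open repair, against 30–33 in the intervention arm. Power is low: at ICC 0.10 the first two figures in item 3 fall to 36–37% and 25–26%.
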